#### Recruitment Methods:

Subjects will be screened for eligibility based on chart review conducted prior to their scheduled appointment. If eligible they will be contacted in advance of their appointment to determine their interest in participation. If they are interested in participating, they will be verbally consented and randomized prior to the appointment. This will be performed remotely by the study coordinator. A message will be sent to the provider they are seeing and a note placed in the medical record to designate their participation and treatment arm. The patient will then be seen by their National Center for Advanced Pelvic Surgery provider, whom are listed as sub-investigators on the project.

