#### Study Endpoints:

The primary endpoint will be patient satisfaction scores related to their treatment for chronic pelvic pain. Secondary endpoints will be quality of life and pain scores.

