#### Study Intervention:

Patients randomized to the intervention arm will receive standard care in addition to a Chronic Pelvic Pain Handbook which outlines their diagnoses and includes educational materials, an individualized treatment plan and follow up schedule.

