#### Procedures Involved:

Patients meeting eligibility criteria will be approached regarding their interest in participating. Should they choose to participate they will be randomized using a random number generator- an odd number will designate randomization to the control group, while an even number will designate randomization to the intervention group. Those in the control arm will receive standard care which is individualized based on their specific needs and may include medical, procedural or surgical interventions. Those in the intervention arm will receive standard care in addition to our Chronic Pelvic Pain Handbook which includes educational resources pertinent to their specific diagnosis, defines available treatment resources, provides a clearly defined follow up schedule and points of contact. Resources included in the Chronic Pain Handbook were thoroughly reviewed by the study team and providers within the National Center for Advanced Pelvic Surgery team. They were screened to be sure that medically accurate information was being presented and that recommendations reflect best practices for the treatment of chronic pelvic pain based on expert consensus. The diagnoses designated on page 4 of the handbook will be filled out by the provider the patient is seeing in the office. Baseline demographics will be collected in addition to validated surveys measuring quality of life and pain scores for all participants. These surveys will be repeated at 3 months, 6 months and 12 months following initial enrollment. Patients' satisfaction with their treatment will also be measured at 3 months, 6 months and 12 months.

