#### Data Collected:

Baseline demographic and pain related data including age, race/ethnicity, BMI, age when pain started, prior treatments, smoking status, history of anxiety/depression/sexual assault, current or prior engagement in psychotherapy, family history of chronic pain will be collected through chart review and patient interview at time of their scheduled visit.

Measurements of pain and quality of life will be collected through previously validated questionnaires regarding pelvic pain (Yosef et al, 2016), in addition to the PHQ-9, GAD-7, Pain Catastrophizing Scale, and Pain Self Efficacy Questionnaire.

Patient satisfaction data will be collected using the PSQ-18 with additional questions included regarding specific barriers they have experienced, what web based or mobile applications they have used and the degree to which they found them helpful.

The number of visits outside of scheduled follow ups, as well as number of patient portal messages sent between visits will be obtained through chart review.

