#### Consent Process:

The consents will be performed over the phone in advance of the patient's scheduled appointment. If they were not able to be contacted in advance of the appointment the consent may be performed in person.

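### Randomizing by phone before the appointment allows patients who never attend to hold an arm without receiving the intervention or any post-randomization care at this center

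*Protocol*

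**What the plan says.** **Order of steps.** The protocol's Recruitment Methods section has eligible patients contacted ahead of their visit: "If they are interested in participating, they will be verbally consented and randomized prior to the appointment". It adds: "This will be performed remotely by the study coordinator". The provider is then messaged and a note of the arm goes into the record, after which attendance is taken for granted: "The patient will then be seen by their National Center for Advanced Pelvic Surgery provider". Consent Process makes the phone the default and allows one exception: "If they were not able to be contacted in advance of the appointment the consent may be performed in person".

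**What the arm consists of.** Study Intervention describes standard care plus a "Chronic Pelvic Pain Handbook which outlines their diagnoses and includes educational materials, an individualized treatment plan and follow up schedule". Procedures Involved ties part of it to the visit: "The diagnoses designated on page 4 of the handbook will be filled out by the provider the patient is seeing in the office".

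**What is measured.** Study Endpoints states: "The primary endpoint will be patient satisfaction scores related to their treatment for chronic pelvic pain". Data Collected names the instrument: "Patient satisfaction data will be collected using the PSQ-18 with additional questions included regarding specific barriers they have experienced". Under Procedures Involved, satisfaction is measured at 3, 6 and 12 months only, and the quality-of-life and pain surveys are timed from initial enrollment. Data Collected places the interview part of the baseline history at the scheduled visit.

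No section makes attendance a condition of randomization or says what happens to a randomized patient who does not attend.

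**The concern.** The arm is fixed at a point when nothing that defines it has yet happened. A pain score exists whether or not the patient comes to the clinic, but a rating of treatment needs treatment. For a phone-randomized patient who never attends, a satisfaction form can still be completed, but it would describe care received earlier or elsewhere. It could not reflect the difference between handbook and standard care.

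Keeping these patients in the comparison pulls the estimated effect toward zero. Dropping them means excluding patients after randomization. That costs precision and, under conditions the protocol neither states nor rules out, could also bias the comparison. An analysis rule can choose between these two losses, but it cannot supply a rating of care that was not received. The order of steps is set in the protocol itself, so it is not something left to a statistical analysis plan.

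**Working it through.** **Step 1. Trace the two routes.**

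| Step | Phone route (default) | In-person route (fallback) |
|---|---|---|
| Consent | before the visit | at the visit |
| Random draw | before the visit | timing not stated separately, but the patient is already in the clinic |
| Baseline interview | at the visit | at the visit |
| Handbook diagnoses | by the provider, in the office | by the provider, in the office |
| Arm assigned but no visit | possible | not possible |

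Only the phone route can produce a randomized patient with no visit.

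**Step 2. Inputs for size.** The protocol states no sample size, power, effect size, standard deviation or attendance rate, so there is no figure of its own to reproduce. Everything below is assumed: two-sided 5% test, 80% power if all attend, 1:1 allocation, and a share q of all randomized patients who never attend, equal in both arms, with q = 5%, 10% or 20%.

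The noncentrality for 80% power is 1.960 + 0.842 = 2.802.

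**Step 3. Non-attenders kept, with no handbook effect.** The mean difference shrinks by (1 − q), so power = Φ(2.802(1 − q) − 1.960). The sample needed to restore 80% power grows by 1/(1 − q)².

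- q = 5%: Φ(2.662 − 1.960) = Φ(0.702) = 0.759; factor 1/0.9025 = 1.11
- q = 10%: Φ(2.522 − 1.960) = Φ(0.562) = 0.713; factor 1/0.81 = 1.23
- q = 20%: Φ(2.242 − 1.960) = Φ(0.282) = 0.611; factor 1/0.64 = 1.56

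**Step 4. Non-attenders dropped equally from both arms.** The sample shrinks by (1 − q), so power = Φ(2.802√(1 − q) − 1.960).

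- q = 5%: Φ(2.731 − 1.960) = 0.780
- q = 10%: Φ(2.658 − 1.960) = 0.757
- q = 20%: Φ(2.506 − 1.960) = 0.707

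**Step 5. Cross-check with a concrete design.** With an assumed effect of 0.5 SD, 63 patients per arm give 80.1% power. At q = 5%, 10% and 20%, power is 76.0%, 71.4% and 61.2% if non-attenders are kept, and 78.1%, 75.9% and 70.9% if they are dropped. To hold 80% with non-attenders kept takes 70, 78 or 99 per arm. These agree with Steps 3 and 4 to within rounding.

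**Step 6. Bias, only if attendance differs by arm.** If non-attenders would have scored d lower than attenders, dropping them raises an arm's mean by q·d. The comparison (intervention minus control) then shifts by (q₁ − q₀)·d. For example, 5% non-attendance in the intervention arm, 15% in control and d = 0.5 SD give (0.05 − 0.15) × 0.5 = −0.05 SD. All three inputs are assumed. With equal attendance and the same d in both arms, the shift is zero.

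**The case against.** Several points on the other side stand, and they limit the claim.

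- **The endpoint is not confined to this center.** A reader might infer that no non-attender can be scored. The endpoint is satisfaction with treatment for chronic pelvic pain wherever received. Nothing shown limits the trial to new patients, and outside referral is part of current practice. An established patient can fill in the questionnaire. What remains is that the score would not reflect care given after randomization at this center.
- **A missed visit is not permanent non-attendance.** A patient who cancels can rebook within the 12 months. Only those who never come raise the problem, and the assumed 5% to 20% must be read as that group alone.
- **That no handbook is received is an inference.** The protocol says who completes the diagnoses and where, not when the handbook is handed over.
- **Bias is not shown.** A reader might infer that excluding non-attenders biases the result. That would need patients to know their arm before the visit and attendance to depend on it. The protocol says the provider is told; it does not say whether the patient is. If patients do not know, attendance should not depend on arm and exclusion costs only precision. The bias example also gives a satisfaction level to patients whose rating is doubtful, so it indicates scale and no more.
- **The Background does not establish a high rate.** Its remarks on cost, time and doubts about usefulness concern adherence to care already prescribed, not attendance at the index appointment.
- **The loss may be small.** At 5% with non-attenders dropped, power moves only from 80% to 78%.

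None of this disputes the order of steps on the phone route.

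**Conclusion.** The point holds in a limited form. On the default phone route, the protocol permits randomized patients who never attend. By inference they have no completed handbook, and they have had no post-randomization care at this center. Their satisfaction scores, if any, say nothing about the contrast under study, and a patient new to the center may have no treatment to rate.

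The size is unknown from the document. Under the assumptions of 80% planned power and 5% to 20% permanent non-attendance, equal by arm, power falls to about 76% to 61% if these patients are kept with no effect, or about 78% to 71% if they are dropped. Bias is a possibility that the protocol leaves open, not a finding. This does not invalidate the trial; it is a cheap improvement to a stated procedure.

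**What to change.** 1. **Recruitment Methods:** keep phone screening and verbal consent ahead of the visit, but reword so that the random number is drawn only after the patient has arrived for the appointment and completed the baseline surveys.
2. **Procedures Involved:** state that the 3-, 6- and 12-month assessments, satisfaction included, are timed from randomization. Otherwise a phone consent followed by a draw at arrival leaves two possible enrollment dates.
3. **Accounting:** report patients who consent by phone but do not attend as consented and not randomized.

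**Cost.** A protocol wording change. The coordinator must make the draw on the day of the visit, remotely if needed, and notify the provider in time, with the handbook ready. No extra patients, visits or procedures are required. The in-person consent route already involves enrollment on the day, though only as a fallback, so same-day availability would become routine.

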#### Consent Process:

The consents will be performed over the phone in advance of the patient's scheduled appointment. If they were not able to be contacted in advance of the appointment the consent may be performed in person.

